4.1.2 Visit 2 (Confirmation Ragweed Pollen Challenge)

Eligible participants will return to the EEU for a 3-hour pollen exposure. The following procedures will be performed:

- Inclusion/exclusion criteria verification
- Coronavirus disease 2019 (COVID-19) testing via a rapid antigen test for severe acute respiratory syndrome coronavirus-2 (SARS-CoV-2) infection before challenge
- Urine pregnancy testing (for WOCBP only)
- The participants will be exposed to a standard Ragweed pollen concentration of 3500 ± 500 grains/m³ for a period of 3 hours (H0 to H3).
- During pollen exposure in the EEU, participants will rate their allergic symptoms every 15 minutes, starting at zero minutes after start of challenge, until 3 hours after start of challenge. Only those participants with qualifying symptom scores (TNSS-3 ≥ 4) will be eligible to be randomized into the study. In case a TNSS-3 ≥ 4 is not achieved by H3, the participant can be challenged again if deemed appropriate by

the Investigator. If TNSS-3 ≥ 4 is still not achieved with the second session the participant is not eligible for study continuation.

- If in the judgment of the Investigator, symptoms become intolerable the participants will be removed from the EEU.
- After 3 hours of challenge: discharge from the EEU
- e-Diary completion
- Concomitant medication recording
- Participants will be questioned with regards to AEs.

Only those participants with qualifying symptom scores (TNSS-3 ≥ 4) in the last 90 minutes of the challenge will be confirmed for continuing in the study.

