9.5 Sample Size Determination

Number of subjects (N) = 96 randomized participants (86 evaluable participants)

All eligible participants will be randomized into 1 out of 2 Arms with the randomization ratio allocation 1:1 as follows:

- Arm A: two days of pre-treatment with fexofenadine, then fexofenadine 180 mg during the test pollen challenge.
- Arm B: two days of pre-treatment with placebo, then fexofenadine 180 mg during the test pollen challenge.

The primary efficacy endpoint is the AUC of TNSS-3 (including rhinorrhea, sneezing, and nasal itching, where each symptom is scored from 0 to 3) from H0 to H6 at Visit 4. The maximum score of TNSS-3 is 9.²

The expected benefit of the pre-treatment or the variability of the pre-treatment using the AUC of the TNSS-3 were not published in the literature when the pre-treatment with fexofenadine before allergen exposure has been evaluated.²⁰ Therefore, given the previous study LPS15332 using TNSS-3, the mean (SD) of the AUC_{h2-h12} of the TNSS-3 has been estimated to be equal to 26.34 (16.66) on the placebo group and 18.53 (13.73) on the fexofenadine group after 3 hours of pollen exposure in the period 3, thus a common SD, estimated to be equal to 15, has been used for the sample size calculation.¹⁴ An MCID is commonly defined as a 0.55 change on Total Nasal Symptoms Score of 4 symptoms (TNSS-4) when 4 individual symptoms (ie, rhinorrhea, nasal congestion, nasal itching, and sneezing) are measured.¹⁶

Assuming a common SD=15 and a targeted effect size of 0.70 for the primary endpoint, it will correspond to a difference of AUC of TNSS-3 between Arm A and Arm B of 10.5, which may be interpreted as a difference of TNSS-3 around 2 points between 2 Arms at each time point (which is higher than the MCID of TNSS-3 with 3 individual symptoms). Therefore, at least 86 evaluable patients in both, Arm A and B (ie, included in the mITT population, meaning 43 patients in each arm) are needed to detect a 0.70 effect size for the additional benefit of two days of pre-treatment with fexofenadine on the SAR symptoms with 90% of power and a 2-sided type I error of 5%, using a 2-sample t-test which is assumed to be roughly equivalent

to the primary analysis that will be planned. This sample size has been calculated using EAST6.5 software.

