7.1. Adjustments for Covariates and Factors to be Included in Analyses

The following covariates and factors are used in the analyses. For details of their inclusion in the models, see the specific analysis section.

- TNSS-3 at Day 1/Visit 4 H0
- (Total Ocular Symptoms Score) TOSS at Day 1/Visit 4 H0
- (Total Symptoms Score) TSS at Day 1/Visit 4 H0
- Individual symptoms score at Day 1
- Treatment group (Fexofenadine 180 mg, Placebo)
- Time point (H0 to H12)
- Treatment group by time point
- Stratification factor – Visit 2 TNSS-3 (TNSS-3 ≤7, TNSS-3 >7)

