16.1.3. Primary Analysis of Primary Efficacy Variable(s)

The primary efficacy analysis will be performed for the mITT.

The primary analysis will be the comparison of the primary efficacy endpoint (ie, AUC of the TNSS-3 from H0 to H6 at V4) between fexofenadine and placebo, using an analysis of covariance (ANCOVA) with treatment group as fixed effect and the baseline value of TNSS-3 (i.e., at H0 at V4) as covariate. The mean TNSS-3 and its 95% CI will be plotted across time from H0 to H6 at Visit 4. This plot will also include the LS mean and 95% CI of the AUC.

Document:	[REDACTED]	
Author:	Version Number:	[REDACTED]
	Version Date:	[17Feb2023]
Template No.:	Reference:	[REDACTED]
Effective Date:		[REDACTED]
[REDACTED]		

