16.2.3. Analysis of Secondary Efficacy Variables

16.2.3.1. ANALYSIS OF SECONDARY VARIABLES BASED ON AUC

All secondary endpoints based on the AUC (i.e., TNSS-3 and TOSS) will be analysed using an ANCOVA model,

Document:	[REDACTED]	
Author:	Version Number:	[REDACTED]
	Version Date:	[17Feb2023]
Template No.:	Reference:	[REDACTED]
Effective Date:	[REDACTED]	
[REDACTED]		

with treatment group as fixed effect and the baseline values as covariate. For the AUC assessment starting from Randomization (D1) to D4, symptom scoring at D1 will be used as baseline.

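### The primary ANCOVA leaves out the continuous Visit 2 challenge response, a pre-randomisation covariate that could add precision for one degree of freedom; the size of the gain is unknown.

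*SAP*

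**What the plan says.** The primary endpoint is the TNSS-3 AUC from H0 to H6 at Visit 4. SAP 16.1.3 analyses it by ANCOVA "with treatment group as fixed effect and the baseline value of TNSS-3 (i.e., at H0 at V4) as covariate", and Protocol 9.3.2 gives the same model. For the AUC-based secondary endpoints, SAP 16.2.3.1 fits an ANCOVA "with treatment group as fixed effect and the baseline values as covariate".

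At Visit 2, under Protocol 4.1.2, "participants will rate their allergic symptoms every 15 minutes, starting at zero minutes after start of challenge", up to 3 hours. Pollen concentration (3500 ± 500 grains/m³) and planned duration match Visit 4 (Protocol 4.1.6). Only participants who reach TNSS-3 ≥4 in the last 90 minutes go on. A participant who misses the threshold may be challenged once more, and one with intolerable symptoms may be removed early.

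SAP 7.1 lists "Stratification factor – Visit 2 TNSS-3 (TNSS-3 ≤7, TNSS-3 >7" among its covariates and factors, but refers to the specific analysis sections for what enters each model, and 16.1.3 does not name this factor. SAP 10 reports the same two-level split as a baseline characteristic. SAP 3.3 adds an exploratory analysis stratified at the same cut of baseline TNSS-3.

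**The concern.** Visit 2 records how strongly each person reacts to the challenge that is repeated at Visit 4, before any study drug is given. It is an obvious candidate predictor of the Visit 4 AUC. The one score covariate in the primary model, Visit 4 H0, is a single rating as exposure starts, outside ragweed season. It may say little about reactivity to pollen, although the documents give no data on this.

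If Visit 2 predicts Visit 4 beyond what H0 carries, leaving it out keeps explainable between-person variation in the residual. The confidence interval is then wider, and power lower, than the collected data allow. The secondary efficacy endpoints are tested only if the primary is significant (SAP 7.5), so precision on the primary test affects them too.

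**Working it through.** **Inputs.** Protocol 9.5: "Assuming a common SD=15 and a targeted effect size of 0.70 for the primary endpoint"; a "difference of AUC of TNSS-3 between Arm A and Arm B of 10.5"; participants "included in the mITT population, meaning 43 patients in each arm"; two-sided 5% level; 90% power; two-sample t-test. Visit 2 ratings at 0, 15, …, 180 minutes: 180/15 + 1 = 13 if the session is completed. The documents give no Visit 2 to Visit 4 correlation, so r is an assumption, shown from 0 to 0.6.

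**The plan's own figure.** SE = 15 × √(2/43) = 3.235, and 10.5/3.235 = 3.246. The normal approximation gives Φ(3.246 − 1.960) = 90.1%, so 43 per arm reproduces. The exact noncentral t gives 89.4%. Dropout: 86/0.90 = 95.6, rounded up to 96 randomised, which also reproduces.

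**Adding Visit 2.** The residual SD becomes 15 × √(1 − r²). The SE and the width of the interval shrink by the factor √(1 − r²). Power is noncentral t with non-centrality 10.5/SE and 86 − 3 = 83 degrees of freedom. Counting the Visit 4 H0 term as well (82) changes power by no more than 0.01 percentage points.

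| r | residual SD | SE | CI narrower by | power |
|---|---|---|---|---|
| 0 | 15.00 | 3.235 | 0% | 89.4% |
| 0.1 | 14.92 | 3.219 | 0.5% | 89.7% |
| 0.2 | 14.70 | 3.170 | 2% | 90.6% |
| 0.3 | 14.31 | 3.086 | 5% | 92.0% |
| 0.4 | 13.75 | 2.965 | 8% | 93.8% |
| 0.5 | 12.99 | 2.802 | 13% | 95.9% |
| 0.6 | 12.00 | 2.588 | 20% | 98.0% |

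**How to read r.** The table takes 15 as the SD left after the planned covariate, so Visit 4 H0 gets no credit, as in the protocol's own sizing. The matching r is the partial correlation given Visit 4 H0. If r is read as the marginal correlation, the gains are upper bounds, because H0 may already carry part of the signal. The SD of 15 comes from an AUC over h2-h12 in an earlier study, so the SE and power columns share that uncertainty. The percentage narrowing does not depend on it.

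**If the stratum is also fitted.** A two-level cut of a normal predictor keeps about 64% of its explained variance at a 50% split and 34% at a 10% split. Take r = 0.5 before the stratum is fitted.
- At the 64% share, the stratum explains 0.64 × 0.25 = 0.16 and power is already 93.8%. The continuous score then adds about 2 points and narrows the interval by 1 − √(0.75/0.84) = 5.5%.
- At the 34% share, the stratum explains 0.34 × 0.25 = 0.085 and power is 91.8%. The continuous score then adds about 4 points and narrows the interval by 1 − √(0.75/0.915) = 9.5%.

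**The case against.** The strongest reply is that nothing is broken. The sample size takes no credit for any covariate, 43 per arm delivers about the stated power, and leaving out Visit 2 makes the test neither biased nor invalid. All of that stands. A reader might infer that the trial is underpowered or its primary test unsound because of this omission; the documents support neither inference.

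The second reply is that the benefit is speculative. This also stands as regards size. The protocol's background section supports a positive correlation only qualitatively, by saying that the exposure unit was developed for reproducible symptoms. Several design features may lower r:
- Entry at TNSS-3 ≥4 restricts the range, and the score is capped at 9.
- Half of the primary AUC (H3 to H6) falls after exposure and after fexofenadine in both arms, and Visit 2 has no counterpart to it.

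A reader might therefore take a gain at r = 0.4 to 0.6 as the expected result. The documents give no basis for preferring that range to lower values.

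Thirteen ratings per person are not assured, because of early removal. Nor can one say that no analysis anywhere uses the continuous Visit 2 scores, since the exploratory efficacy text is redacted; the statement holds for the visible primary and secondary models. Protocol 6.3.1 places randomisation at Visit 2, against Visit 3 elsewhere. That needs reconciling, but qualifying at Visit 2 is a condition for randomisation, so the qualifying scores come first.

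What does not stand is that the choice is mere preference. The covariate is measured before randomisation, is already collected, and leaves power at 89.4% even if r is 0.

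**Conclusion.** The point holds as one of efficiency. The primary ANCOVA adjusts for a single Visit 4 H0 rating and not for the continuous Visit 2 response. The gain is near nil for r up to about 0.2 (power 90.6%, interval 2% narrower), modest at 0.3 to 0.4, and material at 0.5 to 0.6. These figures assume a difference of 10.5, SD 15 and 43 per arm. They shrink by the share that Visit 4 H0, or a fitted Visit 2 stratum, already explains. For the Visit 4 TOSS AUCs a gain in the same direction is expected from the Visit 2 TOSS response, but it is not quantified. Nor is it for the H0-H12 windows, where nine of the twelve hours follow exposure and dosing. The change is worth making because its cost is negligible, not because a particular gain is assured.

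**What to change.** Before unblinding, amend SAP 16.1.3 to add the Visit 2 TNSS-3 AUC from H0 to H3 as a continuous covariate alongside the planned terms. Specify:
- that the AUC is taken from the qualifying Visit 2 session when a participant was challenged twice;
- how early removal and missing Visit 2 ratings are handled, for example by the interpolation and carry-forward rule of SAP 7.3 applied up to H3. A time-average over a truncated session covers mainly the build-up of symptoms and may under-score the strongest reactors.

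In SAP 16.2.3.1, use the Visit 2 TOSS AUC in the same way for the Visit 4 TOSS AUC endpoints.

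The cost is SAP wording, one derived variable per score and one degree of freedom per model, with no new data. SAP 3.3 states that the SAP supersedes the protocol's statistical methods, so SAP wording is enough.

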16.1.4. Supplementary Analysis of Primary Efficacy Variable(s)

Not applicable.

16.1.5. Sensitivity Analysis of Primary Efficacy Variable(s)

The primary analysis will be performed for observed cases.

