4.3. Final Analysis

All final, planned analyses identified in this SAP will be performed by IQVIA Biostatistics following Sponsor Authorization of this Statistical Analysis Plan, Database Lock, Sponsor Authorization of Analysis Sets and Unblinding of Treatment.

Document:	[REDACTED]	
Author:	[REDACTED]	Version Number: [REDACTED]
		Version Date: [17Feb2023]
Template No.:	[REDACTED]	Reference: [REDACTED]
Effective Date:	[REDACTED]	
	[REDACTED]	

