5.6. Modified Intent-To-Treat Analysis Set [mITT]

The modified intent-to-treat analysis set (mITT) will contain all eligible, ITT, and treated subjects with Total Nasal Symptoms Score of 3 symptoms (TNSS-3) evaluation at H0 at V4 and at least a further time point at Visit 4. Subjects will be classified according to randomized treatment.

Document:	[REDACTED]	
Author:	Version Number:	[REDACTED]
	Version Date:	[17Feb2023]
Template No.:	Reference:	[REDACTED]
Effective Date:	[REDACTED]	
[REDACTED]		

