7.3. Missing Data

Missing safety data will not be imputed.

A missing symptom score will be imputed using linear interpolation between the last available preceding value and the first following non missing value; if no following non-missing value is available, the last available value will be carried forward up to H+12. Baseline value will not be extended in case of all post baseline values are missing.

Document:	[REDACTED]	
Author:	[REDACTED]	Version Number: [REDACTED]
		Version Date: [17Feb2023]
Template No.:	[REDACTED]	Reference: [REDACTED]
Effective Date:	[REDACTED]	
[REDACTED]		

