9.1. Disposition

Subject disposition and withdrawals, and reasons for exclusion from each analysis set, including inclusion and exclusion criteria will be summarized for the ENR set. The primary reason for discontinuation of study, including any of the following, will be summarized by treatment group:

- Screen Failure
- Adverse Event
- EEU challenge intolerance
- Poor Compliance to Protocol
- Study Terminated by Sponsor
- Patient Withdrew Consent
- Investigator Decision
- Death
- Other

A listing of all subjects who discontinued from the trial and their reason for discontinuation will be provided.

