16. EFFICACY OUTCOMES

16.1. Primary Efficacy

16.1.1. Primary Efficacy Variable & Derivation

The primary efficacy endpoint is AUC (Area under the curve) of TNSS-3 from H0 to H6 at Visit 4.

The TNSS-3 is a composite score calculated as the sum of rhinorrhea, sneezing, and nasal itching scores (maximum 9). The individual scores are collected in e-diary.

The AUC will be computed using the linear trapezoidal method provided in reference section 22 (Ref 3) (22).

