16.1.2. Intercurrent Event Handling and Data Imputation for Primary Efficacy Variable(s)

Not applicable.

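### Does the undefined term in the observed-case rerun of the primary AUC leave a choice open that could matter?

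*SAP*

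**What the plan says.** The primary variable is the trapezoidal AUC of TNSS-3 from H0 to H6 at Visit 4 (SAP 16.1.1). It is compared by ANCOVA in the mITT set with the H0 score as covariate (SAP 16.1.3). TNSS-3 sums three items, and "The individual scores are collected in e-diary".

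SAP 7.3 fills a missing symptom score by linear interpolation between the neighbouring recorded values; "if no following non-missing value is available, the last available value will be carried forward up to H+12". SAP 16.1.2, whose heading covers imputation for the primary variable, reads only that it does not apply. SAP 16.1.4 (supplementary analysis) and 7.4 (intercurrent events) read the same way.

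SAP 16.1.5 says in full: "The primary analysis will be performed for observed cases". The mITT set in SAP 5.6 asks for a TNSS-3 "evaluation at H0 at V4 and at least a further time point at Visit 4". SAP 4.3 places "Sponsor Authorization of Analysis Sets and Unblinding of Treatment" after database lock, and the sets in section 5 include no observed-case set.

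**The concern.** An observed case is easy to identify for a single measurement, but not for an area built from 19 scores. The term could mean:

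- all 19 scores recorded;
- a score recorded at H6;
- no value carried forward;
- an AUC cut off, or rescaled, at the last score.

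These keep different people or give them different values. The mITT set admits very short profiles, and SAP 16.1.5 is the only planned check on the carry-forward rule. Because the subset is not an analysis set, the sign-off in SAP 4.3 does not visibly cover it, so in principle it could be settled with treatment codes known. Sections 16.1.2 and 7.3, read literally, also disagree on whether the primary AUC is imputed at all.

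At stake is whether the rerun informs a reader about carry-forward, or only reflects lost numbers or a chosen definition.

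**Working it through.** **The plan's own figure.** Protocol 9.5 uses SD 15, difference 10.5 (effect size 10.5/15 = 0.70), two-sided 5% and 90% power. Per arm: n = 2 × (1.960 + 1.282)² / 0.70² = 42.9, so 43 per arm and 86 in total. Dropout of 10%: 86/0.90 = 95.6, so 96. Both match. Exact t-test power at 43 per arm is 0.894. None of this depends on SAP 16.1.5.

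**Score grid.** Protocol 4.1.6: every 15 minutes from H0 to H3 gives 13 points; every 30 minutes to H6 adds 6; total 19. Hourly home scores follow to H12.

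**Gaps between recorded scores.** Interpolated points lie on the straight line that the trapezoid already draws, so the area is the same. On a test profile with H1.0 and H1.25 removed, both routes gave 27.0.

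**Profiles that stop early.** Take an assumed profile: 0 at H0, linear to 6 at H1.5, flat to H3, linear to 2 at H6.

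- Full AUC: 4.5 + 9 + 12 = 25.5.
- Last score at H1.5, carried forward: 4.5 + 6 × 4.5 = 31.5.
- Cut off at H1.5: 4.5.
- Rescaled to 6 hours: 4.5/1.5 × 6 = 18.0.

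Carry-forward and cut-off differ by 27.0 for this person. If 10% of one arm stopped this way (assumed), that arm's mean would differ by 2.7, or 2.7/10.5 = 26% of the design difference. But 4.5 is an AUC from H0 to H1.5, and the rescaled value is a different variable again. Section 16.1.5 repeats the primary analysis, whose variable runs from H0 to H6, so neither fits.

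**Who is kept.** H0 is guaranteed by the mITT definition. With an assumed independent miss rate p at each other point:

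| p | All 19 recorded: 86 × (1−p)^18 | H6 recorded: 86 × (1−p) | Nothing carried forward through H6: 86 × (1−p^7) |
|---|---|---|---|
| 0.5% | 78.6 | 85.6 | 86.0 |
| 1% | 71.8 | 85.1 | 86.0 |
| 2% | 59.8 | 84.3 | 86.0 |
| 5% | 34.2 | 81.7 | 86.0 |

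The last column differs from the third because SAP 7.3 carries a value forward only when nothing later exists up to H12. A missed H6 followed by any score at H7 to H12 is interpolated. Carry-forward at H6 therefore needs seven misses in a row (H6 to H12), and 0.05^7 is below one in a billion. Independence is the assumption that most separates the columns; clustering of misses in the same people shrinks the spread.

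**Longest carry-forward.** A participant with only H0 and H0.25 has 5.75/6 = 96% of the AUC carried, but only if every later score through H12 is also missing.

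**Item or sum.** For a single-item gap, the two recorded items can differ from their interpolated values by up to 6 points together. Multiplied by the point's trapezoid weight:

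- 15-minute point: 0.25 × 6 = 1.5.
- H3: 0.375 × 6 = 2.25.
- H3.5 to H5.5: 0.5 × 6 = 3.0.
- H6: 0.25 × 6 = 1.5.

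In an arm mean of 43, at most 3.0/43 = 0.07 units, or 0.07/10.5 = 0.7% of the design difference. A gap in two of the three items also makes the levels differ, but only one recorded item is then at issue: at most 0.5 × 3 = 1.5 units.

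**Section 16.1.2 beside 7.3.** Section 7.3 leaves safety data unimputed and gives a rule for symptom scores on the H0 to H12 clock, which exists only at Visit 4. That rule has no use except in the efficacy AUCs and score curves. The parallel sections 16.2.2 and 16.3.2 carry the same not-applicable entry, which fits a template answer meaning nothing beyond 7.3. A rerun on observed cases also presupposes that the main run imputes.

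**The case for a change.** The strongest argument for a change is that a sensitivity analysis should be reproducible from the SAP, that this is the only one for the primary endpoint, and that a few lines of text would settle it before unblinding. Early stopping is contemplated: investigators may remove participants with intolerable symptoms (Protocol 4.1.6), and "EEU challenge intolerance" is a listed reason for discontinuation (SAP 9.1). Such missingness would be related to symptoms, and cutting the AUC at the last score would reward it with a low value.

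Part of this stands. The term is undefined in the public text, and the rerun is best described as named but not fully specified. The rest is weaker.

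- The discontinuation list covers everyone who consented, alongside screen failures, so that entry may concern the Visit 2 challenge.
- Removal from the unit need not end scoring, because the e-diary runs on a phone or supplied device and participants are discharged only after H6.
- The table templates named in SAP section 8 accompany the SAP but are not public and may define the subset. A choice made after unblinding is therefore possible but not shown.
- A short definition is easy to get wrong. Excluding anyone with a carried-forward value would still count as observed a participant with only H0 and H12, whose scores between them are all interpolated.

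**Conclusion.** No change follows. This is a gap in detail that analysts fill sensibly, together with a clerical entry in section 16.1.2 that section 7.3 overrides. Under Protocol 9.1 the study is positive if the primary null hypothesis is rejected in favour of active pre-treatment. Under SAP 7.5 the secondary tests open on the primary result alone. The observed-case rerun feeds neither, so its power under any assumed miss rate has no bearing on the trial's conclusion. With the endpoint fixed as H0 to H6, the workable choices are all 19 scores recorded or a recorded H6. Both use the same ANCOVA, and a reader can judge either from the number of participants analysed.

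The primary AUC rule and the 86 evaluable participants are unaffected, and the level of imputation moves an arm mean by at most 0.07 units for one single-item gap. The conclusion rests on section 7.3 governing the primary AUC, and on the cut-off AUC being ruled out by the endpoint's own definition. The documents give no rates of missed scores, removal or rescue, so the profile and rates used above are assumptions.
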